**PROTOCOL SUMMARY**

Sponsor	The University of Washington
Protocol Title	Branched Thoracic Endovascular Grafts for the Treatment of Thoraco-abdominal Aortic Aneurysms (B-TEVAR)
Study Description	
An investigator-initiated, prospective, consecutively enrolling, non-randomized single institution clinical evaluation of the safety and effectiveness of either: 1) physician modification of a currently FDA- approved off the shelf thoracic aortic stent graft (COOK Zenith® TX2®); or
 
2) Thoracoabdominal Custom Branch/Fenestrated Endovascular Stent-Graft (Cook Medical); or 3) Cook t-Branch Endovascular Stent Graft or 4) Cook Low Profile (LP) t-Branch or Custom Made Device (CMD) to preserve branch vessels when used in the treatment of patients with thoraco-abdominal aortic aneurysms.

Study Objectives	
The primary objectives of this study are to determine whether physician modified branched endovascular grafts are a safe and effective method of treating patients with thoraco-abdominal aortic aneurysms.
 
The safety of physician modified endovascular grafts will be determined by evaluating the proportion of patients that experience a rate of Major Adverse Events.
 
The effectiveness of physician modified endovascular grafts will be determined by evaluating the proportion of patients that achieve Treatment Success at 12 months post-procedure.

Study Primary Endpoints	
The primary safety endpoint is defined as the proportion of subjects who experience a Major Adverse Event within 30 days of the B-TEVAR procedure.
 
The primary effectiveness endpoint is the proportion of subjects that achieve Treatment Success. Treatment Success is a composite endpoint assessed at 12 months following implantation of the B-TEVAR device that requires the following criteria to be met:
 
 
• Technical Success, defined as successful delivery and deployment of the physician modified graft with preservation of unimpeded flow to those branch vessels intended to be preserved.
 
• Freedom from Type I & III endoleaks
 
• Freedom from stent graft migration
 
• Freedom from aortic aneurysm enlargement
 
• Freedom from aortic aneurysm rupture
 
• Freedom from conversion to open repair
 

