#### 6.5 Post-Treatment follow-up period

The following assessments and tests will be performed at the following intervals:

Time period post-treatment	Acceptable visit timeframe allowance
1 Month (30 days)	± 14 days
6 Months (180 days)	± 30 days*
12 Months (365 days)	± 45 days
Annually from 2 to 5 years	± 60 days

\*This will not be done for those undergoing TEVAR only

- Physical exam
- Laboratory testing to assess renal function and, if needed, to measure CBC
- Contrast Enhanced Spiral CT of the Chest/Abdomen/Pelvis OR for patients unable to receive IV contrast, a non-contrast thin cut CT scan of the Chest/Abdomen/Pelvis will be performed as well as a duplex of the abdominal aorta to assess the branch patency, velocity and to look for the presence of endoleak and aneurysm sac size (\* for subjects undergoing the TEVAR first stage, no aortic duplex will be performed)
- Device/aneurysm assessment based on imaging (endoleak, migration, integrity, patency, TAAA dimensions)
- Concomitant medications - anticoagulants, anti-platelets, antibiotics, statins, Beta-blockers and ACE inhibitors/ARBs
- Adverse events
- Other relevant data as indicated on the CRF including optional wound assessment.

The above assessments are recorded in the appropriate **Follow-up CRF**.

All subjects who have undergone the B-TEVAR device implantation, whether in a single or multiple stage will be followed with the B-TEVAR Follow-up CRF and will be analyzed as a

single group as well as by subgroup of device type. The date of implantation of the modified device will serve as the start time for follow up. Subjects who do not undergo the second stage of a planned staged repair will be analyzed separately and evaluated for survival and cause of death. With the exception of data points specific to the branched graft (i.e. branch complications, migration, etc.) the same clinical data points will be recorded for patients who only undergo the first stage of a staged repair, including medical demographics, aneurysm size and extent, and major adverse events. Additional information for the TEVAR alone will include a rationale as to why the second stage was not completed. For the two staged approach, the time interval between Stage 1 and Stage 2 will be recorded. Complete data will be reported for each group. Outcomes based on subgroup analysis of those who had single repair, staged repair and those who only had the initial stage and did not complete the second stage will also be reported.

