### **8.14 Technical Failures**

In the event that a branched stent graft could not be deployed due to a technical failure, device failure information will be captured on the **Device Failure CRF**.

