#### 9.1.2 Effectiveness

The primary effectiveness endpoint is the proportion of treatment group subjects that achieve treatment success with the B- TEVAR procedure, whether via the staged approach or done as a single procedure . Treatment success is a composite endpoint assessed at 12 months after the B-TEVAR procedure is performed that requires all of the following criteria to be met in order for a patient to be considered a treatment success:

- Technical Success, defined as successful delivery and deployment of the endovascular graft with preservation of unimpeded flow to those branch vessels intended to be preserved.
- Freedom from Type I & III endoleak. Type I and III endoleaks will be assessed by the investigator using Spiral CT images.
- Freedom from stent graft migration. Migration of the aortic stent graft is defined as evidence of proximal or distal movement of the stent graft >10 mm relative to fixed anatomic landmarks. Migration of a branch is defined as movement of the stent in relation to fixed anatomic location that results in a Type I or III endoleak. Spiral CT images will be used by the investigator to determine migration from the one month (baseline) CT image.
- Freedom from TAAA enlargement. Sac enlargement is an increase in aneurysm diameter (>5 mm) from the one month (baseline) post-operative measurement will be considered TAAA enlargement, as determined by the investigator.
- Freedom from TAAA rupture
- Freedom from conversion to open repair

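### Section 6.5 defines the B-TEVAR analysis group and time zero by device implantation, while section 9.1.2 counts treatment group subjects from the procedure, so the place of a failed delivery in Treatment Success is unsettled

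*Protocol*

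**What the plan says.** Section 6.5 states: "All subjects who have undergone the B-TEVAR device implantation, whether in a single or multiple stage will be followed with the B-TEVAR Follow-up CRF". The same sentence makes these patients the single pooled group for analysis and the basis of the analyses by device type. On the time origin it says: "The date of implantation of the modified device will serve as the start time for follow up". The only other group it sets up is the incomplete staged repairs: "Subjects who do not undergo the second stage of a planned staged repair will be analyzed separately and evaluated for survival and cause of death".

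Section 9.1.2 defines the primary effectiveness endpoint in other terms: "The primary effectiveness endpoint is the proportion of treatment group subjects that achieve treatment success". On timing it says: "Treatment success is a composite endpoint assessed at 12 months after the B-TEVAR procedure is performed". Its first required component is "Technical Success, defined as successful delivery and deployment of the endovascular graft", together with open flow to the target branches. The Protocol Summary gives the same composite a different anchor: "assessed at 12 months following implantation of the B-TEVAR device".

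Section 8.14 covers the failed graft itself: "In the event that a branched stent graft could not be deployed due to a technical failure, device failure information will be captured". The form it names is the Device Failure CRF. The section does not say how the patient counts in either primary endpoint.

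**The concern.** Treatment Success is meant to penalise a graft that cannot be delivered or deployed. An analysis group made up only of implanted patients has already passed most of that test. A patient taken to the B-TEVAR operation who leaves without a branched graft has no implantation date. This applies to a single-stage patient and to one at an attempted second stage. Neither is named in the pooled group of section 6.5. Nor do they clearly fit its other group, which is for patients who never underwent the second stage.

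If section 6.5 were used to form the denominator, the delivery part of Technical Success would be met by everyone analysed, and Treatment Success would be reported too high. The second objective in section 1.0, the ability to deliver the graft, depends on the same denominator.

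**Working it through.** **Texts side by side**

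| Place | Who is counted | Time origin |
|---|---|---|
| 6.5 | patients who had device implantation | implantation date |
| Summary, effectiveness | subjects | implantation |
| 9.1.2 | treatment group subjects | procedure |
| Summary, safety | subjects | procedure |
| 6.1, Step 4 (follow-up CRF) | patients having the B-TEVAR operation | procedure |

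Section 9.1.2 does not settle the matter alone. The Treatment Group is 60 patients (section 5.2.1), and the Summary counts them by planned approach. It therefore includes staged patients who may never reach the second stage, whom section 6.5 analyses separately. The two sections already differ on the denominator before any delivery fails.

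**Size for Treatment Success**

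The protocol gives no delivery failure rate and no expected success rate, so there is no planned figure to reproduce. Assume that all 60 patients have an attempted B-TEVAR. Let f be the number of failed deliveries and x the number of successes, all among the implanted.

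- Rate under a literal 6.5: x/(60 − f)
- Rate with every attempt counted: x/60
- Difference: [x/(60 − f)] × f/60

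With about 80% success among the implanted (x rounded to whole patients):

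| f | Implanted only | All attempted | Difference (points) | Delivery success, all attempted |
|---|---|---|---|---|
| 1 | 47/59 = 79.7% | 47/60 = 78.3% | 1.3 | 59/60 = 98.3% |
| 3 | 46/57 = 80.7% | 46/60 = 76.7% | 4.0 | 57/60 = 95.0% |
| 6 | 43/54 = 79.6% | 43/60 = 71.7% | 8.0 | 54/60 = 90.0% |

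For f = 3 the exact 95% intervals are 68.1–90.0% and 64.0–86.6%. As success among the implanted runs from 70% to 90%, the difference is 1.2 to 1.5 points at f = 1, 3.5 to 4.5 at f = 3, and 7.0 to 9.1 at f = 6. One patient can move the rate by at most 1/60 = 1.7 points at f = 1.

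**How likely is a failure?**

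The branched-graft series of 81 and 189 patients in section 2.1.4 report 100% implant success. With no failures in n, the one-sided 95% upper bound is 1 − 0.05^(1/n):

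- n = 189: 1.6%, or about 0.9 expected in 60
- n = 81: 3.6%, or about 2.2 expected in 60

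The chance of at least one failure in 60 is 1 − (1 − q)^60. For true rates q of 1%, 2% and 5% this is 45%, 70% and 95%.

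**Safety**

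Assume 3 failed attempts, and 12 patients with a major adverse event (MAE) among the other 57. The implanted-only rate is 12/57 = 21.1%. With all attempts counted it is 14/60 = 23.3% if two of the three have an MAE, and 12/60 = 20.0% if none has. The direction is not fixed.

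**The case against.** The strongest reply is that section 6.5 is a follow-up section. Its contrast is between patients who had the branched operation and those who had only the first-stage TEVAR, not between delivered and failed grafts. The protocol also uses implant loosely for the operation, for example in section 6.3, and section 8.13 speaks of conversion at the initial implant procedure. Step 4 of section 6.1 assigns the B-TEVAR follow-up form by procedure. The endpoint section, 9.1.2, is the natural authority, and under it a failed delivery fails the composite.

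Much of this stands. A reader might infer that failed deliveries are excluded and that Technical Success can never register one. No text says so. Access and delivery success are recorded at the procedure (6.3), undeployable grafts have their own form (8.14), and so do conversions (8.13). Technical Success can also fail on branch flow in an implanted patient.

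A reader might also infer that deaths and blood loss after a failed attempt leave the 30-day MAE rate. The Summary anchors that endpoint to the procedure, as section 8.15 does for aneurysm-related death. For safety, only the section 6.5 denominator is in doubt. The screen failures for small iliac arteries in section 2.1.4 are no evidence of failed deliveries, because those patients were not treated.

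The reply does not remove the conflict. Section 6.5 does more than schedule visits: it names the group to be analysed and fixes its time zero, and the Summary repeats the implantation anchor for effectiveness. The undertaking in section 2.1.4 to follow and report all enrolled patients does not place a failed attempt in either primary rate. Section 8.6 adds to the ambiguity by defining conversion only for a patient already implanted. A statistical analysis plan may define the sets, but the protocol should not give two rules for one endpoint.

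**Conclusion.** The point holds as an inconsistency that could favour the device, not as a demonstrated exclusion. Sections 6.5 and 9.1.2 give different denominators and time origins for the primary effectiveness endpoint, and the protocol does not say which governs. A literal section 6.5 would remove delivery failures from an endpoint meant to count them. Section 9.1.2 alone would count them as failures.

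The size is unknown. It is roughly 1 to 2 points per failed delivery, and a few points in all if failures are as rare as the cited series suggest. These figures rest on assumed failure counts, assumed success rates, and all 60 patients reaching an attempted B-TEVAR. The objective on deliverability can still be answered from the procedural data, provided that attempts form the denominator.

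**What to change.** - **Section 6.5:** define the B-TEVAR analysis group as all subjects in whom the B-TEVAR procedure is begun, whether or not a graft is implanted, with time zero at the procedure date.
- **Sections 9.1.2 and 8.14:** state that non-delivery or non-deployment is a failure of Technical Success and of Treatment Success, and that these subjects' 30-day MAEs count in section 9.1.1.
- **Section 9.1.2:** state that treatment group subjects means this set. Subjects who have only the first stage stay in the separate report that section 6.5 already provides.
- **Protocol Summary:** time Treatment Success from the B-TEVAR procedure instead of from implantation.

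An implanted-only analysis can be kept as supportive. The cost is protocol wording, and a reported success rate that may be slightly less favourable.

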Another subset of patients with TAAA appear quite frail at initial presentation. Such patients are clearly not candidates for open repair. Based on the data from Scotland reported above, nearly half of patients referred for TAAA are deemed ineligible for open repair. Furthermore, as has been described in prior reports on B-TEVAR and EVAR, the Dacron used in the Cook Zenith stent graft can induce an inflammatory reaction. The severity of this reaction appears to correlate with extent of aortic coverage as well as the size of the excluded aneurysm, as sac thrombosis and platelet activation combine to cause a severe consumptive coagulopathy. Peri-operative deaths have been attributed to this inflammatory reaction and consumptive coagulopathy in prior reports. Furthermore, staging the procedure for long extent of aortic coverage may help reduce the incidence of spinal cord ischemia. A single animal model has shown reduce SCI with a staged

approach, and some investigators are currently incorporating this into their practice. Incidence of any spinal cord injury was 13% among patients with Type 2 TAAA undergoing staged aortic coverage and 22% among those undergoing a single stage procedure. Those patients who do not tolerate the TEVAR procedure will undergo no further procedure and will be left incompletely treated. If the patient is not healthy enough to tolerate a TEVAR procedure, they cannot be expected to tolerate additional aortic coverage with B-TEVAR. For those who are able to go on to the second stage, the TEVAR stage may help reduce the morbidity of complete aortic coverage in a single sitting.

Staging the TEVAR to precede the B-TEVAR procedure can be both diagnostic and therapeutic. It serves to help clarify the patient's physiologic reserve to determine what, if any, second stage is optimal for that individual. Furthermore, regardless of whether the second stage is performed with open or endovascular technique, it is expected to result in a lesser physiologic stress than repairing the entire TAAA in a single stage. A staged approach may be the safest way for a frail patient with a long extent TAAA to be treated.

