Patients will be enrolled in B-TEVAR study with a plan for 2 different pathways to treatment, either in single sitting or in a staged approach. For those patients in whom a staged approach is planned or considered, consent will be obtained and the patient enrolled prior to undergoing the TEVAR 1st stage of the procedure. These patients will be tracked with a separate follow up case report form at 1 and 12 months and annually to 5 years or until they undergo the second stage with a branched device, at which time their outcomes will be followed according to the routine case report forms. Some patients who undergo the 1st stage will not go on to have the second stage done with a branched graft. This could be due to the determination that they can indeed tolerate open repair, or due to a complex recovery after the 1st stage TEVAR. Such patients will be followed up to 5 years after enrollment. All patients who are enrolled will be followed and reported on. Patients who undergo the first stage, but not the second stage, will be reported as a sub-group of patients in the annual report.

All patients who undergo the first stage TEVAR will be treated with the same TX2 device that is in the B-TEVAR protocol. The specific peri-visceral device used for the second stage could be any one of the 5 device options, CMD, t-Branch, LP CMD or t-Branch or physician modified.

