#### Step 1: Principle Investigator Evaluation

The PI will perform a history and physical examination and review any pertinent pre-operative studies, including the CT angiogram. Based on this review, the PI will make a determination as to whether or not the patient meets the inclusion/criteria, whether they are “high risk” for open repair, whether the aneurysm anatomy is amenable to repair with B-TEVAR, and whether a single or two-staged procedure is appropriate.

The decision about single vs. staged procedure will be individualized to each subject. The determination will depend on length of aortic coverage, size of the aneurysm, and access anatomy. A single staged procedure is preferable in cases with short aortic coverage (lower risk of spinal cord injury and coagulation abnormalities), large aneurysms (at increased risk of interval rupture), and subjects with difficult access (as re-operation may be complicated by re-operative / difficult access). In each case, the PI will attempt to balance these issues to optimize patient safety and minimize risk. There are insufficient data at this time to prescribe absolute parameters to this decision process, and the decision must be based on best physician judgment.

As discussed in section 4.0.3, device selection will be made based on a balance of the urgency of treatment as well as the specific patient anatomy. For patients requiring urgent treatment, (i.e. those with very large aneurysms or those presenting with symptoms concerning for impending rupture) or patients who must travel long distances and cannot make multiple trips, the physician modified device or the pre-manufactured t-Branch device would be used. The physician modified device is customizable and can be used in small aortic flow channels and can be deployed from femoral access only. The t-Branch device, on the other hand, has downward oriented cuffs which may facilitate implantation in a large aneurysm sac, but it requires brachial artery access. For patients who are deemed to be able to wait the 6-8 weeks for graft manufacture and can make the requisite multiple trips to the University of Washington, they will be treated with the commercially manufactured custom device. It is expected that a majority of subjects will be treated with the commercially manufactured custom device.

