### Step 4: Procedure

The patient will then proceed to have their procedure. The process will differ for single vs. two-staged procedures.

- A) For single staged patients, this first operation will be the B-TEVAR procedure. Their post-operative follow up will follow the protocol as described below, with clinic visits, labs and imaging done at 1, 6, 12 months and annually to 5 years. The B- TEVAR Follow up CRF will be used.

B) For two-staged patients, this first operation will be the TEVAR procedure. Their post-operative follow up will utilize the TEVAR Follow Up CRFs. They will be seen with imaging studies at 1 and 12 months and annually until 5 years or until they proceed with the B-TEVAR second stage. After the patient undergoes the B-TEVAR procedure, they will continue with the routine study follow up at 1, 6, 12 months and annually to 5 years after the B-TEVAR procedure using the B-TEVAR Follow Up CRFs.

The decision to proceed with the second stage will be at the discretion of the PI. That determination will be based on when the patient has returned to their pre-operative level of functional status, their laboratory values have stabilized/recovered, they remain free from major organ system dysfunction as a consequence of the first stage, and the patient agrees to undergo a second operation. If the patient's recovery is complicated by a permanent decline in functional status, or permanent organ system dysfunction (e.g. long term nursing facility residency, permanent spinal cord injury, end-stage renal failure on dialysis), then the PI will determine that the second stage should not proceed. These patients will then continue follow up using the TEVAR CRF until their condition improves and they can undergo the B-TEVAR procedure or they complete 5 years of follow up. As described below in the Risk Analysis, section 10.0, such patients who do not complete the second stage will be left with an incompletely treated aneurysm and will remain at risk of rupture and death. This will be explained in detail to the subjects prior to enrollment.

Step 1

PI Evaluation:

- a) Meet all Inclusion and no Exclusion Criteria
- b) High risk for open repair
- c) Anatomically eligible for B-TEVAR
- d) Single vs. multiple staged repair

Step 2

2nd Attending Physician Evaluation:

- a) Patient has a reasonable expectation of survival after operation
- b) Patient has a reasonable expectation of survival to 1 year with successful repair

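### The staged-repair results in Section 6.5 include only subjects who recovered from stage 1, so they understate the risk of the staged strategy

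*Protocol*

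**What the plan says.** The single or two-stage plan is set before enrolment: at Step 1 of Section 6.1 the PI decides eligibility, anatomy "and whether a single or two-staged procedure is appropriate". Where staging is planned or considered, Section 2.1.4 states that "consent will be obtained and the patient enrolled prior to undergoing the TEVAR" first stage.

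Step 4 makes stage 2 depend on recovery from stage 1. On proceeding, it says: "That determination will be based on when the patient has returned to their pre-operative level of functional status". Laboratory recovery, freedom from major organ dysfunction and the patient's agreement are also required. After permanent harm such as spinal cord injury or dialysis, "then the PI will determine that the second stage should not proceed". Section 2.1.4 agrees: "Those patients who do not tolerate the TEVAR procedure will undergo no further procedure and will be left incompletely treated".

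Section 6.5 then fixes the analysis:
- Time zero: "The date of implantation of the modified device will serve as the start time for follow up".
- Non-completers: "Subjects who do not undergo the second stage of a planned staged repair will be analyzed separately and evaluated for survival and cause of death".
- Reporting by pathway: "Outcomes based on subgroup analysis of those who had single repair, staged repair and those who only had the initial stage", the last group being those who did not complete the second stage.

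The primary safety endpoint (Section 9.1.1) counts MAEs at 30 days after the branched repair.

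**The concern.** The staged-repair subgroup is defined by having got through stage 1. Subjects who died, were permanently harmed or did not recover are moved to another group. Some of the harms that block stage 2 are of the same kind as the MAEs being counted, so the group is filtered on something close to its own outcome.

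Completers' own stage 1 events are lost as well. A subject who has a myocardial infarction or a 1,000 cc blood loss at stage 1, recovers and goes on to stage 2 has an MAE that enters neither the implant-clocked staged rate nor the first-stage-only group. An interval death cannot appear in the staged group at all, although Section 10.0 recognises that risk.

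A clinician choosing a staged approach needs the risk of the whole path from the first operation. Section 2.1.4 presents staging as possibly the safest course for frail patients with long-extent disease and cites spinal cord injury of 13% with staging against 22% without. Readers are therefore likely to take this study's pathway results to that question, and the specified groups do not give a rate that answers it.

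**Working it through.** The protocol states no figure to reproduce. It gives 60 subjects but no MAE rate for stage 1 and no expected split between pathways. All rates below are assumptions.

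**1. Where events are counted under Section 6.5**

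| Event in a planned-staged subject | Staged-repair rate | First-stage-only group |
|---|---|---|
| Death or permanent harm at stage 1, no stage 2 | no | yes |
| Death in the interval | no | yes |
| MAE at stage 1, recovered, stage 2 done | no | no |
| MAE within 30 days of the branched implant | yes | no |

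**2. Size of the understatement**

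Let m1 be the MAE risk at stage 1 and m2 the MAE risk within 30 days of the branched implant. The subgroup shows m2. The planned path carries m1 + (1 − m1) × m2, so the understatement is m1 × (1 − m2).

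With m2 = 20%:
- m1 = 5%: 0.05 + 0.95 × 0.20 = 24%
- m1 = 10%: 0.10 + 0.90 × 0.20 = 28%
- m1 = 20%: 0.20 + 0.80 × 0.20 = 36%

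| | m1 = 5% | m1 = 10% | m1 = 20% |
|---|---|---|---|
| m2 = 10% shown | 14.5% | 19% | 28% |
| m2 = 20% shown | 24% | 28% | 36% |
| m2 = 30% shown | 33.5% | 37% | 44% |

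The formula adds nothing for interval events and treats everyone without a stage 1 MAE as going on to stage 2.

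**3. Does selection settle the comparison with single repair?**

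Take a frail share f. Stage 1 MAE risks are a1 (frail) and b1 (fit); branched-procedure MAE risks are a2 and b2. Assume that any stage 1 MAE stops stage 2, and that case mix is the same in both pathways.

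- Single = f × a2 + (1 − f) × b2
- Completers = [f(1 − a1)a2 + (1 − f)(1 − b1)b2] / [f(1 − a1) + (1 − f)(1 − b1)]
- Planned path = f[a1 + (1 − a1)a2] + (1 − f)[b1 + (1 − b1)b2]

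With b1 = 5% and b2 = 10% throughout:

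| f, a1, a2 | Single | Completers | Planned path | Single / completers |
|---|---|---|---|---|
| 30%, 30%, 40% | 19.0% | 17.2% | 27.5% | 1.105 |
| 30%, 20%, 30% | 16.0% | 15.3% | 23.4% | 1.045 |
| 50%, 30%, 40% | 25.0% | 22.7% | 36.2% | 1.100 |
| 50%, 20%, 30% | 20.0% | 19.1% | 29.2% | 1.045 |

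Selection alone makes completers look about 1 to 2 points better than single repair and leaves out about 8 to 14 points of planned-path risk. The last column is the break-even: if staged subjects' baseline risk is more than about 1.05 to 1.10 times that of single-stage subjects, completers look worse than single repair.

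**The case against.** The strongest reply is that nothing is concealed. Section 2.1.4 says all enrolled patients will be followed and reported. Section 6.5 gives first-stage-only subjects their own report, with MAEs, survival, cause of death and the reason stage 2 was not done, and it records the interval between stages. This is a 60-patient feasibility study with no stated test of one pathway against another, and a clock at the implant suits device performance. All of this stands and limits the weight of the point. For deaths, adding the two staged groups comes close to the planned cohort. It does not recover completers' stage 1 MAEs, and no strategy-level rate is specified. Nor is this merely a matter for an analysis plan not shown, since Section 6.5 itself fixes the groups and the clock.

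Four stronger readings are tempting and not supported:

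- **Staged repair will look safer than single repair.** Step 1 prefers single repair for short coverage, which it describes as lower risk, and Section 2.1.4 suggests staging for frail, long-extent patients. That pushes the other way. Section 2.1.4 also lets subjects fit enough for open repair leave after stage 1, so fitter subjects exit too.
- **Grouping by the Step 1 plan is unbiased.** It removes post-enrolment selection only. The plan is PI judgement on coverage length, aneurysm size and access, so confounding by indication remains. The single-versus-staged choice already precedes enrolment; only the split between staged and first-stage-only is made afterwards.
- **This is immortal-time bias.** No event-free time before the implant is credited to the staged group, so the fault is better described as selection into the group.
- **True mortality of the staged path is about 13%.** One could compute 1 − 0.75^(14/52) = 7.45% interval death and, with 6% at the branched procedure, 1 − 0.94 × 0.9255 = 13.0%. But the 25% yearly rupture death in Section 2.0 concerns unoperated patients unfit for surgery, the 14 weeks comes from a ten-patient hybrid series, and Section 10.0 calls the interval risk unknown.

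**Conclusion.** The point holds in a limited form. The staged-repair results are conditional on surviving and recovering from stage 1, and the specified reporting gives no rate for the staged strategy from its first operation. The understatement is m1 × (1 − m2), which is 4 to 16 points for m1 of 5% to 20% and m2 of 20%. These rates are assumed; only the mechanism comes from the protocol. The selection favours the staged group, but the net direction against single repair cannot be determined from the documents. The point does not rest on any claim that first-stage-only subjects go unreported.

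**What to change.** In Section 6.5, add a report by the pathway planned at Step 1 (planned single, planned staged), timed from the first study procedure. Keep first-stage-only subjects in planned staged, and count deaths and MAEs at stage 1, in the interval and at stage 2. Record the plan as one of two categories at enrolment, because Section 2.1.4 speaks of staging as planned or considered.

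Keep the implant-clocked results by completed pathway as a description of device performance, labelled as conditional on reaching stage 2. State that any single-versus-staged contrast is descriptive and confounded by indication.

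The cost is one definition and one more descriptive table. The Step 1 decision and the TEVAR case report forms already supply the data. The staged figure will probably be less favourable.
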